4.3.5 Subgroup analyses

No specific subgroup analysis has been planned as the result of the small number of patients for the study. If sample size permits, subgroup analysis may be conducted by age, race, and patient status on ITI success and relapse after ITI success.

4.4 SECONDARY ENDPOINT(S) ANALYSIS

4.4.1 Key/Confirmatory secondary endpoint(s)

4.4.1.1 Definition of endpoint(s)

ITI Outcome

Each patient will be assigned to one of the following 5 categories of outcomes of ITI treatment.

ITI success

A patient is categorized as an ITI success if the following 3 criteria are all met:

- Confirmed negative titers consisting of 2 consecutive negative inhibitor assessments within 2 weeks (± 3 days) based on local laboratory results <0.6 BU/mL by the Nijmegen-modified Bethesda assay; determination of negative titer based on the Bethesda assay is acceptable at sites that have not yet adopted the Nijmegen-modified Bethesda assay.
- IR ≥ 1.32 IU/dL per IU/kg in 2 consecutive assessments representing $\geq 66\%$ of the expected IR 2 IU/dL per IU/kg.
- $t_{1/2} \geq 7$ hours.

Early withdrawal (outcome not determinable) during ITI period

Unable to determine ITI outcome due to withdrawal prior to completing ITI Period (48 weeks of ITI treatment). For these patients, their status will be further categorized into:

- Positive inhibitor titer
 - Inhibitor titer reduced ($\geq 20\%$) from baseline but not yet negative
 - Inhibitor titer remains the same ($\pm 20\%$) as baseline
 - Inhibitor increased ($\geq 20\%$) from baseline
- Negative inhibitory titer
- Negative inhibitory titer and normal IR

ITI treatment failure (those with at least 36 weeks or 48 weeks of ITI treatment)

Treatment failure is defined for the following two scenarios:

- Patients complete at least 9 months of ITI treatments (Week 36 [Month 9] visit) and experience no downward trend of $\geq 20\%$ in the inhibitor titer comparing to titer at the end of the initial 3 months of treatment (Week 12 [Month 3] visit).
- Patients completed 48 weeks of ITI treatment and inhibitor titer remains positive (≥ 0.6 BU/mL) at Week 48 (Month 12) visit including those who achieve the first negative titer at Week 48 (Month 12) but are not confirmed with a consecutive second negative tier and subsequently with IR ≥ 1.32 IU/dL per IU/kg or $t_{1/2} \geq 7$ hours after 48 weeks of ITI treatment

Patients who have been determined to have failed ITI will then proceed to the End of Treatment (EOT) Visit.

Partial success

The determination of partial success will be made only among patients who have completed the ITI period (Week 48 [12 months] visit) but do not fulfill the criteria for ITI success or treatment failure.

Partial success is defined as achieving negative inhibitor titer and one of the PK parameters of ITI success: IR ≥ 1.32 IU/dL per IU/kg OR $t_{1/2} \geq 7$ hours.

Patients who have been determined to have achieved only partial success will then proceed to EOT Visit.

Ongoing

This category is only applicable for the interim analysis for the patients who do not meet the definitions for the 4 categories of ITI outcomes as described above. For patients who are ongoing, their status will be further categorized into:

- Positive inhibitor titer
 - Inhibitor titer reduced ($\geq 20\%$) from baseline but not yet negative
 - Inhibitor titer remains the same ($\pm 20\%$) as baseline
 - Inhibitor increased ($\geq 20\%$) from baseline
- Negative inhibitory titer
- Negative inhibitory titer and normal IR

The ITIFAS will be used for this analysis.

Occurrence of relapse after successful ITI

Occurrence of relapse is defined as the proportions of patients who reach ITI success and later meet criteria of relapse during the Tapering Period, Follow-up Period, and the two Periods combined.

Relapse

Relapse is defined as confirmed positive inhibitor titer ≥ 0.6 BU/mL and IR < 1.32 IU/dL after tolerance is achieved, during the Tapering or Follow-Up Periods. The samples for IR derivation need to meet the criteria of 24-hour wash-out period.

Results from local lab will be used for this determination. In the event that the local lab results are not available, the results from the central lab will be used. Occurrence and dates of positive inhibitor titer and loss of normal IR will be recorded in the eCRFs by the investigator.

Time to Relapse

This is defined as the number of days from the date of ITI success to the date of the first confirmed case of relapse.

Number of bleeding episodes

Annualized rate of the number of bleeding episodes during ITI Period will be calculated for each patient in the ITIFAS who had been observed for at least 90 days:

$$\text{annualized bleeding rate} = \frac{\text{number of bleeding episodes}}{(\text{length of study period in days}/365.25)}$$

Bleeding Episode

If a break-through bleed is not resolved right away, a patient may make multiple reports of the same bleed. To determine if multiple reports of bleeds belong to the same bleeding episode, the following definition is to be used.

Bleeds which receive treatment(s)

A bleeding episode is considered to start from the first report of bleeding. Additional reports of bleeds at the same location will be considered as the same bleeding episode if the injection to treat the bleed occur ≤ 72 hours of the previous infusion. A reported bleed will be considered a new bleeding episode if the infusion to treat the bleed occurs > 72 hours after the previous infusion to treat a bleed in the same location.

Any bleeding at a different location is considered a separate bleeding episode, regardless of the time from the last injection.

Bleeds which were un-treated

After the first report of bleeding, subsequent reports from the same location will be considered as the same bleeding episode if they occur ≤ 72 hours from the previous report of bleed. Reports of bleeding events > 72 hours after the previous report of a bleed at the same location will be considered a new bleeding episode.

Spontaneous Bleeding Episode

Bleeding episodes are classified as spontaneous if a parent/caregiver records a bleeding event when there is no known contributing factor such as a definite trauma or antecedent “strenuous” activity. The determination of “strenuous” is at the discretion of the Investigator, and the parent/caregiver/patient will be instructed on this by the Investigator.

Traumatic Bleeding Episode

Bleeding episodes are classified as traumatic if the parent/caregiver records a bleeding episode even when there is a known or believed reason for the bleeding. For example, if a patient exercises strenuously and then has a bleeding episode in the absence of any obvious injury, the bleeding episode will still be recorded as traumatic. Target joint bleeding episodes can be traumatic if a known action leads to bleeding into the joint. The Investigator considers whether events resulting in a traumatic bleeding episode qualify as AEs and reports as such.

Number of days away from work or school

If sample size permits ($n \geq 5$), number of days missed from school or work per month will be calculated.

Number of hospitalization days

If sample size permits ($n \geq 5$), number of hospitalization days per year will be calculated.

Adherence

Percentage of administered doses as registered in the EPD and EDC versus the prescribed doses and percentage of number of days with infusions as registered in the EPD and EDC compared with the prescribed number of days will be calculated.

Adherence to the treatment regimen at each period is defined in 2 ways. Dose adherence is defined as the percentage of administered doses as registered in the EPD and EDC versus the prescribed doses to a patient. Dosing frequency adherence is defined as the percentage of number of days with infusions as registered in the EPD and EDC compared to the prescribed number of days to a patient in that period.

Consumption during ITI

Consumption of rFVIIIFc at each period is defined as the total rFVIIIFc in IU/kg which is received by a patient in that period.

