#### Treatment failure

Treatment failure is defined as fulfilling one of the following criteria:

- No downward trend of at least 20% in the inhibitor titer in a 6-month (24-week) period after the initial 3 months (12 weeks) during the ITI Period (assessed at the Week 36 [Month 9] Visit).
- Presence of a sustained positive inhibitor ( $\geq 0.6$  BU/mL) after 48 weeks (12 months) of ITI treatment.
- Negative inhibitor titer without achieving either of the 2 PK parameters of ITI success after 48 weeks (12 months) of ITI treatment:
  - $IR \geq 1.32$  IU/dL per IU/kg OR
  - $t_{1/2} \geq 7$  hours

Subjects who have been determined to have failed ITI will then proceed to the End of Treatment (EOT) Visit.

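### SAP 4.4.1.1 has no outcome category for a 48-week completer who turned inhibitor-negative before Week 48 and met neither PK criterion, whom the protocol classes as a treatment failure

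*SAP*

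**What the plan says.** Protocol 7.2.2.2 lists three alternative failure criteria. The third reads "Negative inhibitor titer without achieving either of the 2 PK parameters of ITI success after 48 weeks (12 months) of ITI treatment", the parameters being IR ≥1.32 IU/dL per IU/kg and half-life ≥7 h. It sets no limit on when the titer first turned negative and does not ask for a confirmed negative.

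The SAP, whose version history says it rests on the same protocol, opens its definition in 4.4.1.1 with "Treatment failure is defined for the following two scenarios". Scenario 1 is the absence of a 20% titer fall between Week 12 and Week 36. Scenario 2 is a titer still positive at Week 48. It is extended to patients whose first negative titer is at Week 48 "but are not confirmed with a consecutive second negative tier and subsequently with IR" or half-life at the required level. That extension is all that remains of the protocol's third criterion.

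The same section promises a complete classification: "Each patient will be assigned to one of the following 5 categories of outcomes of ITI treatment".

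**The concern.** A classification that claims to place every patient should have no empty cell, and it should agree with the protocol it implements. Here one group that the protocol defines as failures meets no SAP definition. If the outcome table is programmed from the SAP, these patients drop out of the failure row and the final rows need not add to the full ITIFAS. If the table uses the investigator's recorded outcome instead, it will show failures that match neither SAP scenario. Describing the outcome of ITI treatment is a secondary objective, and the failure proportion is part of that description.

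**Working it through.** No power, alpha or sample-size formula bears on this point. The check sets the definitions side by side.

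**Profile.** The patient:
- completes 48 weeks of ITI;
- is first negative before Week 48 and negative at Week 48, confirmed or not;
- has a titer fall of at least 20% from Week 12 to Week 36;
- has no IR ≥1.32 IU/dL per IU/kg at any assessment;
- has not shown a half-life ≥7 h.

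**Step 1: each SAP category at the final analysis.**

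| SAP 4.4.1.1 category | What it needs | Met? |
|---|---|---|
| ITI success | confirmed negative titer, IR and half-life | No |
| Partial success | "Partial success is defined as achieving negative inhibitor titer and one of the PK parameters of ITI success" | No, neither PK parameter |
| Failure, scenario 1 | no 20% fall, Week 12 to 36 | No |
| Failure, scenario 2 | positive at Week 48, or first negative at Week 48 | No |
| Early withdrawal | "Unable to determine ITI outcome due to withdrawal prior to completing ITI Period" | No, he completed |
| Ongoing | "This category is only applicable for the interim analysis" | No |

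SAP 4.4.1.2 also names an *undetermined* row but does not define it. The only outcome that 4.4.1.1 calls not determinable is early withdrawal.

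**Step 2: the protocol.** The third criterion in 7.2.2.2 classes this patient as a treatment failure.

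**Step 3: does the gap depend on how the SAP is read?** Two wordings are open.
- The end of scenario 2 can mean that lack of confirmation applies to the second titer and the PK results together (reading A), or to the second titer only (reading B).
- IR can mean a single value, as the partial-success text allows, or a confirmed one, as SAP 4.3.1 requires.

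Take completers with a confirmed negative titer and a fall of at least 20%: 2 titer courses (first negative before Week 48; at Week 48 and confirmed later) × 3 IR states (none, single, confirmed) × 2 half-life states (reached; not reached or not done) = 12 states. Those with no SAP category:

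| | Single IR counts | Confirmed IR needed |
|---|---|---|
| Reading A | 1 of 12 | 2 of 12 |
| Reading B | 2 of 12 | 4 of 12 |

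The profile with a confirmed early negative, no IR and no half-life is in every cell. The other uncovered states depend on the reading.

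The unconfirmed version lies outside this grid and is also uncovered. Protocol 7.2.2 interprets IR only after the negative titer is confirmed, so no IR can count. The patient is neither positive at Week 48 nor first negative then.

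**Step 4: size per patient.**
- Protocol 16.1, up to 17 subjects: 1/17 = 5.9 percentage points.
- SAP section 2, up to 30 patients: 1/30 = 3.3 percentage points.

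**Step 5: after the fix.** With the protocol's third criterion added and one IR definition used for both failure and partial success, 0 of 12 states are uncovered under either reading, and the unconfirmed state becomes a failure too. If failure were judged on a single IR and partial success on a confirmed IR, 2 of 12 would stay uncovered (single IR, half-life not reached, in either titer course). The single IR definition is therefore part of the fix.

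**The case against.** The strongest reply is that the study does have a prespecified outcome for this patient. Protocol 13.1 bases the analysis of ITI outcome on the investigator's assessment entered in the eCRF, and Protocol 7.2.2.2 tells the investigator that he is a failure. The SAP nowhere says that a programmed outcome replaces that entry. This stands. A reader might infer that the outcome is undefined, or would have to be settled after the data are seen. The documents do not support that. What remains is an SAP rule that conflicts with the protocol and with the eCRF outcome, without saying which prevails.

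A reader might also infer that a listed secondary endpoint is damaged. The first one listed is ITI success, and its definition and count are untouched. Nor was the third criterion dropped altogether: scenario 2 keeps it for patients first negative at Week 48, which suggests a drafting slip.

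The profile is also narrow. Half-life is due at the EOT Visit even without normal IR (Protocol Table 1, footnote 14), so some patients would move to partial success. One ground for skipping that test is that the investigator has already judged the patient a failure. The SAP does separate negative titer alone from "Negative inhibitory titer and normal IR" for withdrawn and ongoing patients. Those are states before 48 weeks, so they do not show that completers will end there.

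**Conclusion.** Wrong as written, and minor. SAP 4.4.1.1 omits part of a failure criterion that its own protocol sets, and an outcome derived from the SAP text would undercount failures. The effect is confined to the failure row of the descriptive ITI outcome table, at 5.9 points (N = 17) or 3.3 points (N = 30) per affected patient. The documents give no way to estimate how many there will be, and the number may be zero. The primary endpoint does not use these categories, no hypothesis is tested, and SAP 4.3.4 lists each patient's outcome.

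The conclusion assumes a final analysis and a titer fall of at least 20% from Week 12 to Week 36. Whether the Week 36 rule is meant for patients already negative is a separate matter for the sponsor to reconcile, and nothing here relies on an answer.

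**What to change.** In SAP 4.4.1.1:

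1. Add the protocol's third criterion as a separate failure scenario: negative titer after 48 weeks of ITI with neither the IR nor the half-life criterion met, regardless of when the titer first became negative. Keep it apart from the scenario for patients still positive at Week 48.
2. State whether IR in these definitions means a single or a confirmed value, and apply the same definition to partial success and to failure. The sponsor should reconcile Protocol 7.2.2.2, SAP 4.3.1 and SAP 4.4.1.1 on this. This review does not say which definition is right.

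Together these make the categories exhaustive. The cost is two or three sentences in the SAP and no new data.

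### SAP 4.4.1.1 gives no final outcome category to a 48-week completer confirmed negative before Week 48 with neither PK parameter met, whom the protocol counts as a treatment failure

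*SAP*

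**What the plan says.** Protocol 7.2.2.2 (Treatment failure) makes a subject a failure if any one of three criteria is met:

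1. At the Week 36 visit: "No downward trend of at least 20% in the inhibitor titer in a 6-month (24-week) period" after the first 12 weeks.
2. A sustained positive inhibitor after 48 weeks.
3. "Negative inhibitor titer without achieving either of the 2 PK parameters of ITI success after 48 weeks (12 months) of ITI treatment", the two parameters being IR ≥1.32 IU/dL per IU/kg and half-life ≥7 hours.

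SAP 4.4.1.1 introduces its outcome definitions with "Each patient will be assigned to one of the following 5 categories of outcomes of ITI treatment". For failure it states "Treatment failure is defined for the following two scenarios":

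- Scenario 1 is the Week 36 rule, a fall of less than 20% "in the inhibitor titer comparing to titer at the end of the initial 3 months of treatment".
- Scenario 2 is a titer still positive at Week 48. It also takes in "those who achieve the first negative titer at Week 48 (Month 12) but are not confirmed with a consecutive second negative tier" and a subsequent IR or half-life result that meets the threshold.

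On the remaining categories, the SAP says "Partial success is defined as achieving negative inhibitor titer and one of the PK parameters of ITI success". Early withdrawal is for patients who leave before completing 48 weeks. Of the ongoing category it says "This category is only applicable for the interim analysis". SAP 4.4.1.2 then tabulates the number and proportion in each category on the ITI full analysis set.

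**The concern.** The protocol's third failure criterion applies to any subject who is negative after 48 weeks with neither PK parameter, whenever he became negative. The SAP applies that reasoning only when the first negative titer is at Week 48. A patient who became negative earlier and then stalled is left without a category, in a scheme meant to cover everyone.

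At stake is the failure row of a secondary outcome table. The programmer would have to decide what to do with such a patient: leave him out, place him under the undetermined label that SAP 4.4.1.2 uses, or treat partial success as a residual class. Each choice removes a protocol-defined failure from the failure count, and the decision would be made after the data are known.

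**Working it through.** No figure in the plan is at issue, so the check sets the two definitions side by side and runs constructed patients through both.

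**Step 1. Match the criteria.**

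| Protocol 7.2.2.2 | SAP 4.4.1.1 |
|---|---|
| Week 36: no ≥20% fall over the preceding 24 weeks | Scenario 1: same rule, Week 36 against Week 12 |
| Positive titer after 48 weeks | Scenario 2: same |
| Negative titer, neither PK parameter after 48 weeks | Scenario 2 extension, only if the first negative titer is at Week 48 |

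**Step 2. Test one patient against every SAP category.** Illustrative values: Week 12 titer 8 BU/mL, Week 36 titer 2 BU/mL, first negative at Week 44, confirmed at Week 46, still negative at Week 48, IR below 1.32 and half-life criterion not met.

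- ITI success: no, since it needs both PK parameters.
- Early withdrawal: no, since he completed 48 weeks.
- Failure, scenario 1: no. The fall is (8 − 2)/8 = 75%, which exceeds 20%.
- Failure, scenario 2: no. His titer is not positive at Week 48 and his first negative titer was not at Week 48.
- Partial success: no, since it needs one PK parameter.
- Ongoing: no, since it is for interim analyses only.

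He has no SAP category. Under protocol criterion 3 he is a failure. The same patient with his first negative titer at Week 48 is a failure in both documents, confirmed or not, so the four-week difference alone decides whether the SAP classifies him.

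**Step 3. All PK states for a 48-week completer confirmed negative before Week 48 and not caught by scenario 1.**

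| IR ≥1.32 | Half-life ≥7 h | Protocol | SAP |
|---|---|---|---|
| yes | yes | success | success |
| yes | no | partial success | partial success |
| no | yes | partial success | partial success |
| no | no | failure | none |

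The documents disagree in the last row only. The table counts states and says nothing about how often each occurs.

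**Step 4. Size.** Protocol 16.1 plans up to 17 subjects; SAP Section 2 says up to 30. With the ITI full analysis set as denominator, one patient missing from the failure row lowers the failure proportion by 1/17 = 5.9 percentage points, or 1/30 = 3.3 points.

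**Step 5. The Week 36 rule, checked separately.** Scenario 1 does not require the titer to be positive at Week 36. Write T12 and T36 for the two titers. Being negative at Week 36 means T36 < 0.6; no 20% fall means T36 > 0.8 × T12. Both together require T12 < 0.6/0.8 = 0.75 BU/mL. A patient negative by Week 8 (0.3 BU/mL at Weeks 12 and 36), with normal IR but half-life below 7 hours at Week 48, is then literally a failure under the SAP and equally under the protocol bullet. He is a partial success if Table 1 footnote 2 limits the rule. That footnote places the check at the Week 36 interim visit, and Table 1 ends interim visits at the first negative titer.

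**The case against.** Several points on the other side stand.

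- Protocol 13.1 bases the analysis of ITI outcome on the investigator's assessment entered in the eCRF. Investigators work under the three-criterion protocol, and the SAP states that it is based on that protocol. SAP 4.3.4 lists each patient's outcome individually. An affected patient would probably be noticed. However, the SAP failure definition does not defer to the eCRF outcome; it sets out its own rules, and those conflict with the protocol.
- The neither-parameter state is narrow. The partial-success definition does not ask for two consecutive IR results, IR is sampled at two-weekly visits once negativity is confirmed, and half-life is measured at the end-of-treatment visit unless failure has already been declared or a full assessment was done in the preceding two weeks. This supports a small expected number, not zero.
- The study is descriptive, with no hypothesis testing.

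Two stronger readings are tempting and do not hold. A reader might infer that the SAP drops the third criterion altogether; it does not, because scenario 2 retains it for a first negative titer at Week 48. A reader might also count the missing positive-titer condition in scenario 1 as a second departure from the protocol. The protocol's own Week 36 bullet has the same gap, so this is a shared ambiguity, largely contained by Table 1 footnote 2.

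**Conclusion.** The SAP's failure definition is wrong as written for one group: 48-week completers confirmed negative before Week 48, with neither PK parameter, whom scenario 1 does not catch. The severity is minor. How many patients fall in the group cannot be determined from the documents and is probably small. The per-patient effect in Step 4 rests on the planned maximum numbers; with fewer treated patients, each would weigh more.

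The primary endpoint is not affected, because such a patient is not tolerized and is censored whatever his outcome label. Nor is the ITI success proportion, provided the ITI full analysis set remains the denominator.

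A reader might try to show that the state is common from the International ITI Study figures in Protocol 5.1, where the high-dose medians are 4.6 months to negative titer and 6.9 months to normal recovery. The difference of 2.3 months is not a within-patient lag. The same figures give 3.5 − 2.8 = 0.7 months at the lower quartile and 12.0 − 13.8 = −1.8 months at the upper, so they cannot support any estimate of frequency.

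**What to change.** Add a third failure scenario to SAP 4.4.1.1: the patient completed 48 weeks of ITI, has a negative inhibitor titer, and met neither IR ≥1.32 IU/dL per IU/kg nor half-life ≥7 hours. This restores agreement with Protocol 7.2.2.2 and fills the empty cell in Step 3. It costs one clause and uses data already collected.

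As an optional SAP clarification, limit scenario 1 to patients whose titer is still ≥0.6 BU/mL at Week 36, in line with Table 1 footnote 2. Its reach is small (Week 12 titer below 0.75 BU/mL), and that bound assumes laboratories report numeric values below 0.6. No change to site instructions is proposed: altering who goes to the end-of-treatment visit at Week 36 could be a protocol modification needing ethics approval under Protocol 19.3.
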